SAE	Serious Adverse Event
SAP	Statistical Analysis Plan
SD	Standard Deviation
SF-12	Short Form 12 Health Survey
SOC	System Organ Class
TEAE	Treatment Emergent Adverse Event
TFI	Tinnitus Functional Index
TSCHQ	Tinnitus Sample Case History Questionnaire

SYNOPSIS

NAME OF SPONSOR/COMPANY:	Otonomy, Inc.
NAME OF FINISHED PRODUCT:	OTO-313
NAME OF ACTIVE INGREDIENT(S):	Gacyclidine
Protocol No.: OTO-313-201	
Title of Study: A randomized, double-blind, placebo-controlled Phase 2 study of OTO-313 given as a single intratympanic injection in subjects with unilateral subjective tinnitus	
Study Center(s): Study will be conducted at approximately 55 sites globally	
Study Period: Approximately 20 months	Phase of Development: 2
Study Design: This is a randomized, double-blind, placebo-controlled Phase 2 study to evaluate the efficacy and safety of intratympanic OTO-313. Approximately 140 eligible subjects with unilateral tinnitus will be randomly assigned 1:1 to either 0.32 mg OTO-313 or placebo for intratympanic injection to the affected (study) ear. Randomization is stratified by study site, duration of tinnitus (≥ 2 to ≤ 6 months and > 6 to ≤ 12 months since onset) and by the average of the Tinnitus Functional Index (TFI) score at Screening and Baseline (≥ 32 to ≤ 53 points, ≥ 54 to ≤ 100 points). Subjects will be observed for efficacy and safety for 16 weeks following dosing. An independent Safety Review Committee will review accumulated individual subject safety data to ensure appropriate safety and tolerability of OTO-313 and placebo.	
Study Objectives:	
Primary: 
To determine the efficacy of OTO-313 in subjects with unilateral tinnitus by comparing the proportion of subjects achieving response using the TFI relative to placebo.	
Secondary: 
To determine the effect of OTO-313 across additional secondary measures of efficacy (tinnitus loudness and annoyance NRS, PGIC, SF-12) relative to placebo.To determine the safety and tolerability of OTO-313 in subjects with unilateral tinnitus.	

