
Statistical Methods:
 
Sample Size Justification:
 
The primary endpoint is the percentage of responders, where response is defined as achieving at least a 13-point reduction from baseline in the TFI total score at both Weeks 4 and 8. It was observed from the previous study that the response rate for OTO-313 (0.32 mg) was 43%, and 13% for placebo. Based on these results, the assumed rate of response for OTO-313 is 43% and 18% for placebo, which is the 13% observed response rate in previous study plus 5% inflation for potential placebo response.
 
Assuming a 2-sided test and level of significance of 0.05, 60 subjects in the placebo group and 60 subjects in the OTO-313 group will provide approximately 85% power to detect a treatment difference in favor of OTO-313. It is also assumed that an observed discontinuation rate of 15% will be observed, hence the total sample size for this 2-arm study is planned to be 140 subjects, 70 subjects per arm. These sample size calculations were conducted using EASTv6.5 software with a test for a difference in proportions between two groups.
 
Analyses:
 
The primary endpoint, analyzed using the common risk difference between treatment groups, will be tested using a Mantel-Haenszel test controlling for duration of tinnitus and baseline TFI score at Week 8. The 95% confidence intervals (CI) around the common risk difference will be provided. The risk difference in responses rates will also be compared between treatment groups at Weeks 12 and 16 as secondary analyses.
 
The change from baseline in NRS Loudness, NRS Annoyance, TFI total score, each TFI subscale score, and SF-12 will each be analyzed using a linear mixed-effects model with treatment, study day, treatment-by-study day interaction, gender, and tinnitus duration as fixed effects. The unstructured covariance model will be used. Least-square adjusted means, the estimated difference in adjusted means between treatment groups and associated 95% CIs will be provided. Comparisons between treatment groups will be conducted at each post-baseline visit as secondary analyses.
 
The results of the PGIC will be analyzed using a Cochrane-Mantel-Haenszel mean score test controlling for baseline TFI score and duration of tinnitus. This will be done to compare OTO-313 with placebo.
 
Adverse events, audiometry, tympanometry, otoscopic, and C-SSRS safety endpoints will be summarized descriptively. Changes in vital signs and laboratory parameters will be summarized descriptively.
	

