5.2.3. Randomization Algorithm

Subjects will be randomized in a 1:1 ratio (OTO-313:placebo) of treatment groups using a permuted block randomization algorithm. Randomization is stratified by study site, duration of

tinnitus (≥ 2 to ≤ 6 months and > 6 to ≤ 12 months since onset) and by the average of the TFI score at Screening and Baseline (≥ 32 to ≤ 53 points, ≥ 54 to ≤ 100 points).

The randomization process will be deployed via IRT which is accessible 24 hours a day to authorized users. The subject's randomization number will determine the randomized treatment assignment. Investigational product kits will be labeled with a unique kit number using a separate and independent randomization algorithm. Numbered kits will be dispensed based on the treatment assignment.

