8.1.2. Lead-In Period: Day -14 to Day -1 (+ 5 days)

The subject will record their tinnitus loudness and tinnitus annoyance each day, using the NRS for each symptom, in a diary during the 14-day Lead-In assessment period. Subjects must have completed the tinnitus diary on at least 5 of the last 7 days of the 14-day Lead-in period for eligibility. The additional +5 days of the Lead-in period will not be used for eligibility.

8.1.3. Baseline/Investigational Product Administration: Day 1

The purpose of the Day 1 Baseline visit is to confirm subject eligibility, capture baseline efficacy and safety data, and administer the investigational product.

Once the Lead-in period is complete and the subject has met the eligibility criteria for tinnitus diary compliance, the Day 1 Baseline assessments are performed. Results from the prior and concomitant medications review, urine pregnancy test (for female subjects of childbearing potential), and C-SSRS (“Since Last Visit” version) must be available and reviewed by the Investigator to confirm the subject’s eligibility before randomization.

In addition, the following assessments are to be performed on all subjects prior to dosing to establish Baseline status: medical history (with particular attention to any untoward medical occurrences that would meet the definition of a serious outcome – See [Section 9.1 Serious Adverse Event](#)), vital signs, clinical laboratory tests, TFI (overall score of ≥ 32 on the TFI at Screening and Baseline visits is required for eligibility), SF-12, otoscopy, tympanometry, and audiometry. Once eligibility status is confirmed and the subject is randomized, the investigational product is administered and the remaining Day 1 assessments (i.e., AE monitoring) are completed.

If the subject is no longer eligible, the subject will not be randomized and should be recorded as a screen failure (documentation for screen failures will be limited specifically to end of study reason, demographic information, TSCHQ, reason for screen failure, and inclusion/exclusion criteria). Re-screening of subjects may be permitted after discussion with the medical monitor and sponsor.

All assessments as listed in the Time and Events Schedule ([Table 1](#)) are to be performed at this visit.

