11.4.2.1. Primary Analyses

The primary endpoint is the percent of responders at Week 8, where subjects will be classified as responders if they achieve at least a 13-point reduction from baseline in the TFI overall score at both Weeks 4 and 8. The primary endpoint will be summarized descriptively by treatment group. The percentage of responders will be analyzed using the common risk difference between treatment groups and will be tested using a Mantel-Haenszel test controlling for study site, duration of tinnitus, and baseline TFI overall score. Specifically, comparison between OTO-313 and placebo will be made by testing the following hypothesis:

$$H_0: P_{\text{OTO-313}} = P_{\text{Placebo}} \text{ vs } H_A: P_{\text{OTO-313}} \neq P_{\text{Placebo}}$$

The primary analysis will be conducted for the comparison of OTO-313 and placebo, using a 2-sided test and an alpha level of 5%. The 95% confidence intervals (CI) around the common risk difference will also be provided.

Missing data for the primary endpoint will be imputed using a multiple imputation technique that will be described in detail in the SAP.

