11.4.2.2.1. Additional Responder Analyses

The following additional responder definitions will also be derived for Weeks 12 and 16:

- Week 12 responder #1: achieving at least a 13-point reduction from baseline in the TFI overall score at Weeks 8 and 12
- Week 12 responder #2: achieving at least a 13-point reduction from baseline in the TFI overall score at Weeks 4, 8, and 12
- Week 16 responder #1: achieving at least a 13-point reduction from baseline in the TFI overall score at Weeks 12 and 16
- Week 16 responder #2: achieving at least a 13-point reduction from baseline in the TFI overall score at Weeks 8, 12, and 16
- Week 16 responder #3: achieving at least a 13-point reduction from baseline in the TFI overall score at Weeks 4, 8, 12 and 16

These additional responder secondary endpoints will be analyzed in the same manner as the primary analysis as described in Section 11.4.2.1.

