11.4.2.2.3. Categorical Endpoint Analyses

The results of the PGIC will be analyzed using a Cochrane-Mantel-Haenszel mean score test controlling for study site, baseline TFI score, and duration of tinnitus. This will be done to compare OTO-313 with placebo.

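### Do the uncovered TFI averages between 53 and 54, and a baseline TFI factor without categories in the Mantel-Haenszel tests, call for a change?

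*Combined protocol and SAP*

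**What the plan says.** Randomisation is stratified by site, tinnitus duration and TFI. The TFI factor is the mean of two visits, with one stratum ending at 53 and the next starting at 54: "by the average of the TFI score at Screening and Baseline (≥ 32 to ≤ 53 points, ≥ 54 to ≤ 100 points" (Section 5.2.3). The synopsis (Study Design and Methods) and Section 3 give the same limits. None of these places states a rounding rule. The duration strata in the same sentence do meet, at 6 months.

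The analysis text names a TFI factor but gives no categories:

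- Synopsis, primary analysis: "controlling for duration of tinnitus and baseline TFI score at Week 8".
- Section 11.4.2.1, primary analysis: "controlling for study site, duration of tinnitus, and baseline TFI overall score".
- PGIC: "mean score test controlling for baseline TFI score and duration of tinnitus" in the synopsis and "controlling for study site, baseline TFI score, and duration of tinnitus" in Section 11.4.2.2.3.
- The five additional responder definitions in Section 11.4.2.2.1 "will be analyzed in the same manner as the primary analysis as described in Section 11.4.2.1".

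Section 8.1.3 uses the word Baseline for the dosing visit: "The purpose of the Day 1 Baseline visit is to confirm subject eligibility, capture baseline efficacy and safety data". Section 11.1 leaves detailed methodology to a separate SAP.

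**The concern.** There are two apparent defects.

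First, read literally, the allocation rule has a hole. Scores of 53 at Screening and 54 at Baseline both meet the entry floor of 32, yet their mean of 53.5 belongs to neither stratum. This happens even if every TFI score is a whole number.

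Second, a Mantel-Haenszel test needs categories, and the TFI factor has none. Baseline elsewhere means the Day 1 visit, and Section 11.4.2.1 also uses it as the reference for the 13-point reduction. The factor could therefore be read as a Day 1 score cut somewhere, and not as the two-visit average used to randomise. Some subjects would be classified differently under the two readings, and in a single trial the p-value could fall on either side of 0.05. If that choice were still open after unblinding, the pre-specification of the primary test would be weakened.

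**Working it through.** **1. The plan's own figure.** Inputs from Section 11.5: 43% and 18%, 60 evaluable per arm, two-sided 0.05.

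- Mean rate = (0.43 + 0.18)/2 = 0.305.
- Standard error under the null = √(2 × 0.305 × 0.695/60) = 0.0841.
- Standard error under the alternative = √((0.43 × 0.57 + 0.18 × 0.82)/60) = 0.0809.
- Power = Φ((0.25 − 1.96 × 0.0841)/0.0809) = Φ(1.05) = 85.4%, against the stated 85%.
- Dropout: 120/0.85 = 141.2, so 142 against the planned 140.

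The TFI cut does not enter any of these figures.

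**2. Is the hole reachable?** Yes. With whole-number scores the only mean strictly between 53 and 54 is 53.5. If the 25 items give an index in steps of 0.4 (an assumption), the means 53.2, 53.4, 53.6 and 53.8 are possible.

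**3. How many subjects?** The documents give no TFI distribution, so this rests on assumed normal scores: mean 45 to 65, between-subject SD 12 to 20, within-subject SD 5 to 10, both scores at least 32.

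| Score grid | Share in the hole | Of 140 | Chance of at least one, 1 − (1 − p)^140 |
|---|---|---|---|
| Whole numbers | 0.89 to 1.71% | 1.2 to 2.4 | 71 to 91% |
| Steps of 0.4 | 1.44 to 2.77% | 2.0 to 3.9 | 87 to 98% |

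A second run, with means of 45 to 60, total SDs of 12 to 20 and between-visit correlations of 0.7 to 0.9, gave 1.1 to 1.9% and 1.8 to 3.1%. One or more such subjects is likely, but the number is small.

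**4. Would the two readings classify subjects differently?** If the Day 1 score were cut at 54, 5 to 17% of subjects would sit in a category other than their randomised stratum. No section proposes such a cut; it serves only as a comparator.

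**5. Does that matter for the primary test?** The simulation assumed 120 evaluable subjects, 55 sites, blocks of 4, mean TFI 55, SDs 15 and 7.5, and a log-odds slope of 0, 0.5 or 1.0 per 15 Day 1 TFI points. Strata were duration by TFI, as in the synopsis.

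- Type I error: 4.6 to 5.3% with the randomised stratum, 4.5 to 5.3% with the Day 1 category (simulation standard error about 0.3 points).
- Power with the overall rates held at 43% and 18%: about 84 to 88% under either reading.
- Opposite calls at p < 0.05, same setting: about 2 to 3.5% of trials.

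The overall rates must be held at the planned values. If 43% and 18% are fixed only at a TFI of 55, then at slope 1.0 the overall rates drift to about 48% and 25%. The same formula gives Φ((0.23 − 1.96 × √(2 × 0.365 × 0.635/60))/√((0.48 × 0.52 + 0.25 × 0.75)/60)) = Φ(0.68), about 75% before adjustment. That drift explains simulated power of 77 to 79% and opposite calls near 5%. Both describe a smaller effect than the one planned.

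**6. With site in the strata, as in Section 11.4.2.1.** There are 55 × 2 × 2 = 220 cells, or 140/220 = 0.64 subjects per cell. Opposite calls rise to 15 to 16%. They are already 16.4% at slope 0, where TFI is unrelated to response, against 1.7% without site at the same slope. Sparse site cells cause this, and power is low under either TFI reading (22 to 38% across re-runs). Defining the TFI factor would leave those cells just as sparse.

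**7. The two lists side by side.** Section 5.2.3 gives site, duration and TFI. Section 11.4.2.1 gives site, duration and TFI, in the same order. With a method that needs categories, the ordinary reading is that the analysis uses the randomisation strata.

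**The case for a change.** The strongest case for a change is that a pre-specified primary test should leave no choice that could turn a result after unblinding, and that tidying the wording costs almost nothing. The text available here contains no separate SAP that settles the term. A later analysis definition also would not mend the allocation wording. In Section 8 Baseline means Day 1, so the alternative reading is not fanciful.

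Part of this stands. The limits do leave a hole, at least one subject in it is likely, and the analysis text does not name the stratum. An explicit statement in the SAP would be tidier.

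The rest carries less weight. Any two valid adjustments disagree now and then near p = 0.05, and a rate of 2 to 3.5% with matching type I error and power is not evidence of harm. The hole is closed in practice, because the response system cannot randomise a subject without assigning a stratum, and that assignment is then available to the analyst. The real disagreement over the primary test is that Section 11.4.2.1 includes site and the synopsis does not. That is a separate matter, and settling the TFI wording would not resolve it.

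**Conclusion.** No change follows. The hole is a drafting slip that the randomisation system resolves, and the missing categories are a detail that an analyst would sensibly fill with the randomisation strata. Section 11.1 leaves that level of detail to the SAP.

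About 1 to 3% of subjects have an average in the hole. Allocation, sample size and planned power do not change. At 43% and 18%, with duration by TFI strata, the two readings of the factor give the same type I error and power within simulation noise and opposite calls in about 2 to 3.5% of trials. The 15 to 16% figure belongs to sparse site strata and should not be counted here.

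The share in the hole and the simulated results rest on assumed TFI distributions and an assumed relation between TFI and response. The conclusion also assumes that the response system applies one fixed rule to averages between 53 and 54, and that the analysis uses the stratum it assigned. The mixed model in Section 11.4.2.2.2 is unaffected by the missing categories, since it can take TFI as a continuous score.

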5.3. Blinding

The study will be double-blinded. Each treatment syringe will be prepared according to the detailed instructions in the Pharmacy Manual.

In case of emergency, the blind should be broken for site personnel only if knowing the subject's treatment allocation would facilitate specific medical treatment. In all cases, the Investigator should consult with the medical monitor prior to unblinding, and if not possible as soon as it is practical after unblinding has occurred and treatment initiated.

If the blind is broken, the subject will continue to be followed and evaluated per-protocol. The date, time, and reason for the unblinding must be documented on the appropriate page of the eCRF.

The randomization schedule or blocking factor(s) will not be revealed to study subjects, Investigators, clinical staff, site managers or the Sponsor until all subjects have completed the study and the database has been finalized by the Sponsor.

6. DOSAGE AND ADMINISTRATION

6.1. Investigational Product Administration

OTO-313 or placebo is provided in individual Investigational Product kits. All kits must be stored at 2-8°C until use.

Syringes containing OTO-313 or placebo are prepared in a clean location at room temperature. Refer to the Pharmacy Manual for instructions on OTO-313 and placebo preparation instructions.

OTO-313 or placebo will be administered as a single (0.2 mL volume) intratympanic injection to an affected (study) ear. Only a physician may perform the intratympanic injection.

OTO-313 or placebo should be prepared with a 1 mL luer-lock sterile syringe only. Luer slip tip syringes are not acceptable for use due to the viscosity of OTO-313. Recommended needles are 25, 26, or 27 gauge and typically range from 1.5 to 3.5 inches in length.

The recommended injection procedure for intratympanic administration of OTO-313 or placebo in subjects is as follows. A ventilation hole in the tympanic membrane is not needed due to the small injection volume.

1. Place the subject in a recumbent position with the affected (study) ear upwards.

2. Prior to OTO-313 or placebo administration, confirm the ear to be treated is the affected (study) ear.
3. Anesthetize the tympanic membrane by covering the external surface of the inferior-posterior quadrant with topical lidocaine or lidocaine/prilocaine cream (e.g., [REDACTED] or lidocaine spray or solution) until the tympanic membrane is numb. If applicable, suction away any excess topical preparation. Use of phenol is prohibited for anesthetizing the tympanic membrane ([Section 7.1](#)).
4. Using the prepared syringe, insert the needle (bevel facing) into the inferior-posterior quadrant of the tympanic membrane at the level of the round window, taking care not to insert the needle further than necessary.
5. With the needle bevel facing in the inferior-posterior direction, inject 0.2 mL of OTO-313 or placebo towards the round window.
6. Have the subject remain recumbent for 15 minutes following the injection.

6.2. Compliance

OTO-313 or placebo will be administered by a physician as a single, intratympanic injection at Day 1.

The site will maintain a log of all investigational product received, dispensed, and returned. Investigational product supplies for each subject will be inventoried and accounted for in the study.

7. PRIOR, CONCOMITANT AND SUBSEQUENT THERAPY

Use of all concomitant medications will be recorded in the subject's eCRF. This will include all symptomatic relief medications for tinnitus symptoms, prescription drugs, herbal products, vitamins, minerals, and over-the-counter medications taken within 30 days before Screening, which will be considered prior therapy. COVID-19 vaccination at any time prior to Screening or during the study will also be recorded.

At the discretion of the Investigator, any medication deemed necessary for the welfare of the subject may be continued at stable doses during the study, except for those medications listed in [Section 7.1](#). Any changes in concomitant medications will be recorded in the subject's eCRF.

7.1. Prohibited Therapy During the Study Period

The following therapies are prohibited during the study:

- Phenol for use in anesthetizing the tympanic membrane
- Intratympanic injection other than that outlined in the current study
- Systemic corticosteroids (inhaled and nasal steroids are permitted)
- Other investigational drug(s) or device(s)
- Other NMDA receptor antagonists (e.g., memantine, dextromethorphan). Note, occasional use of dextromethorphan for cough suppression is allowed except during

the period 7 days prior to Baseline and 7 days after the injection of the investigational product.

- Medications known as potentially tinnitus-inducing (e.g., aminoglycosides, ototoxic chemotherapeutic drugs, high doses of intravenous loop diuretics, quinine, high doses of aspirin or other non-steroidal anti-inflammatory drugs). Usage of low doses of aspirin (e.g., daily doses of 81 mg) or low doses of other non-steroidal anti-inflammatory drugs for intermittent pain relief may be permitted at the Investigator's discretion.
- Medications that are considered moderate or strong inducers of CYP2B6 (e.g., carbamazepine, efavirenz, rifampin, and ritonavir)

Use of any of these prohibited therapies will be considered a protocol deviation.

7.2. Other Medications and Therapies

It is recognized that during the study subjects may require use of certain medications for relief of symptoms related to tinnitus or other disease (e.g., worsening depression). Use of the following medication and therapies are permitted during the study:

- Stable doses (taken for \geq 1 month prior to Screening) of antidepressant and anti-anxiety medications are allowed during the study, and
- Stable prior use (\geq 1 month prior to Screening) of over-the-counter supplements, medications for tinnitus (e.g., Gingko biloba, melatonin), nonconventional therapy, and transcranial magnetic stimulation for tinnitus.

No new medications, over-the-counter supplements, or other therapies for tinnitus may be introduced during the study.

Any changes reported by the subjects in concomitant medications, including changes in dose or frequency of dosing, while not considered a protocol deviation, should be recorded in the subject's eCRF.

No new hearing aids, sound/noise therapy devices, or behavioral therapy for tinnitus may be introduced during the study. However, patients using devices or behavioral therapy pre-study are permitted to continue stable use.

- Stable prior use (\geq 1 month prior to Screening) of hearing aids, noise generators, and/or sound therapy devices is allowed and, if utilized, these devices should be used consistently throughout the duration of study.
- Similarly, any behavioral therapy for tinnitus should also be stable (\geq 1 month prior to Screening) and continue throughout the duration of the study.

Any changes in the concurrent use of these devices or behavioral therapy for tinnitus, while not considered a protocol deviation, should be recorded in the subject's eCRF.

